8. STATISTICAL METHODOLOGY AND STATISTICAL ANALYSES

8.1. Statistical METHODS

All PK/PD analyses will be performed by the Pfizer Pharmacometrics/Clin Pharm groups. An analysis plan providing details of these analyses will be provided separately.

No adjustment for multiple comparisons will be made.

8.1.1. Analyses for Categorical Data

8.1.1.1. Descriptive Statistics

Categorical data will be summarized by presenting the counts and percentages with the denominator being the number of subjects in the analysis set in the particular treatment group with non-missing data.

8.1.1.2. Efficacy Analysis

Logistic regression models will be used in the analyses of primary endpoint, as well as several secondary endpoints. The model will include strata, and pooled center as independent variables. Treatment by center, treatment by age stratum, and treatment by body weight stratum interaction will be investigated. If interactions are significant, then exploratory analyses will be undertaken to explain the nature and source of the interaction. However, the reported p-values will be based on the main effects model.

Additional analyses may be performed adjusting for baseline covariates as additive terms to the primary model, if necessary. Results from any additional analyses will not be used as a substitute for the planned analyses, but may be used as supplemental information for the study report.

In addition, a sensitivity analysis excluding 16 subjects from investigative site PPD will be performed on the primary endpoint – Continuous Abstinence Rate from Week 9 through 12 – using the primary analysis model.

This sensitivity analysis will be performed for the following groups:

- Overall study.
- 12-16 year old age stratum.

8.1.2. Analyses for Continuous Data

8.1.2.1. Descriptive Statistics

Continuous variables for baseline demographic and smoking history data will be summarized (n, mean, standard deviation, median, minimum and maximum) by treatment group.

8.1.2.2. Efficacy Analysis

Analysis of the continuous endpoints will be performed by using longitudinal repeated measures models including treatment, visit, age strata, body weight strata, pooled study center, and baseline measure.

SAS PROC MIXED will be used, with an unstructured covariance structure. If the unstructured covariance does not converge, compound symmetric variance structure will be used.

8.2. Statistical Analyses

All efficacy analyses will be based on the Full Analysis Set as described in [Section 5.1](#). Efficacy analyses will also be performed on the Completer Set as described in [Section 5.2](#). Missing values will be handled as explained in [Section 7](#).

All analyses will be performed overall as well as on the age stratum of patients who are 12-16 years of age (with corresponding removal of age strata terms from analysis models).

Subjects in this adolescent study will be considered smokers, regardless of the self reported smoking status, if the urine cotinine test is positive.

8.2.1. Baseline Demographics and Other Baseline Characteristics

Height, weight, BMI, and age at screening will be summarized as continuous measures as described in [Section 8.1.1.1](#). Age group and race will be summarized as categorical measures as described in [Section 8.1.2.1](#). Smoking history information and the Fagerstrom Test for Nicotine Dependence will be summarized as described in [Sections 8.1.1.1](#) and [8.1.2.1](#).

These will be summarized for the following groups:

- Overall study.
- 12-16 year old age stratum.
- 12-16 year old age stratum, ≤ 55 kg weight stratum.
- 12-16 year old age stratum, > 55 kg weight stratum.
- 17-19 year old age stratum.

8.2.2. Compliance

Compliance will be calculated overall as well as by visit as described in [Section 5.6](#). Compliance will be summarized by visit as well as overall. Early termination visits will be windowed as indicated in [Section 6.3](#).

These will be summarized for the following groups:

- Overall study.
- 12-16 year old age stratum.
- 12-16 year old age stratum, ≤ 55 kg weight stratum.
- 12-16 year old age stratum, > 55 kg weight stratum.
- 17-19 year old age stratum.

8.2.3. Primary Efficacy Analysis

The primary efficacy analysis will be analysis of *the 4-week continuous abstinence rate (CAR) from Week 9 through Week 12 of treatment for each varenicline treatment group compared with placebo*.

The 4-week CAR will be summarized by treatment group using descriptive statistics and bar charts.

This will be summarized for the following groups:

- Overall study.
- 12-16 year old age stratum.
- 12-16 year old age stratum, ≤ 55 kg weight stratum.
- 12-16 year old age stratum, > 55 kg weight stratum.
- 17-19 year old age stratum.

The 4-week CAR will be analyzed using a logistic regression model as described in [Section 8.1.1.2](#). Odds ratios and 95% confidence intervals will be shown in plots.

These will be analysed for the following groups:

- Overall study.
- 12-16 year old age stratum (without age strata covariate).
- 12-16 year old age stratum, ≤ 55 kg weight stratum (without age strata or body weight strata covariates).
- 12-16 year old age stratum, > 55 kg weight stratum (without age strata or body weight strata covariates).

While the analysis will be performed for sets listed above, the primary analysis of the primary efficacy endpoint is the overall study.

Statistical hypotheses for the primary endpoint will be tested in an ordered fashion to preserve overall Type I Error. The 1 mg BID group will be tested against placebo, and if a statistically significant difference is observed, the 0.5 mg BID group will be tested against placebo. A p-value of 0.05 will be considered statistically significant in both tests. Both tests will be presented regardless of the p-value obtained.

A sensitivity analysis excluding site **PPD** will be performed based on the primary analysis of the primary endpoint. This site was terminated based on concerns regarding GCP non-compliance.

As a sensitivity analysis of the primary endpoint, multiple imputation methods will be used to evaluate the impact of missing data. Subjects who discontinue the study due to insufficient clinical response, adverse event, or death will be imputed based upon the observed placebo distribution, regardless of randomized treatment assignment. Imputation will be based on age stratum, body weight stratum, pooled study center, and baseline number of cigarettes smoked. Subjects who discontinue the study for other reasons, or who complete the study but have a missing Week 9-12 CAR, will be imputed based on observed subjects in the same treatment group. Imputation will be based on treatment, age stratum, body weight stratum, pooled study center, and baseline number of cigarettes smoked.

A final sensitivity analysis will be performed based on discontinuation from treatment, regardless of study completion status.

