5. STUDY TREATMENTS

5.1. Allocation to Treatment

This is a 52 week, double-blind, parallel group study. Subjects will be randomized to receive 12 weeks of varenicline 1 mg BID, varenicline 0.5 mg BID or placebo in a 1:1:1 ratio using a block randomization within each site. Within each randomized treatment group, subjects who weigh ≤ 55 kg at baseline will receive half the assigned dose strength.

Randomization will be stratified by age group (12-16 vs 17-19). In order to ensure a sufficient number of subjects in the 12-16 year old stratum, the 17-19 year old stratum will be capped at a maximum of 90 subjects.

Investigators will obtain subject identification numbers and study drug assignments utilizing a web-based or telephone call-in drug management system as directed by the sponsor. The web-based or telephone call-in drug management system will provide identification numbers

for the subjects at the screening visit. The web-based or telephone call-in drug management system will also coordinate drug dispensation to subjects at each clinic visit.

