9.1. Sample Size Determination

Although analysis for the primary efficacy endpoint will be model based, the sample size calculation is based on a two-sided Chi-Square test with a 0.05 significance level and a 1:1:1 randomization ratio of varenicline 1 mg BID to varenicline 0.5 mg BID to placebo. The study is powered at 80% or greater to detect varenicline (1 mg BID or 0.5 mg BID dose) vs. placebo differences in the CQR from Weeks 9 through 12. The sample size is based on CQR of 9% and 24% for placebo and varenicline respectively, or an odds ratio of 3.2.

A sample size of 300 subjects randomized to varenicline or placebo in a 1:1:1 (100 to varenicline 1 mg BID, 100 to varenicline 0.5 mg BID, 100 to placebo) will provide approximately 80% power to detect a difference in the primary endpoint between varenicline and placebo groups, assuming a true Week 9-12 CQR of 9% and 24% for placebo and varenicline respectively.

Enrollment will be stratified by age group (12-16 vs. 17-19) and sufficient subjects will be enrolled in the 12-16 year old age group to detect a difference in the primary endpoint between varenicline and placebo groups, assuming a true Week 9-12 CQR of 9% and 29% for placebo and varenicline respectively.

In order to ensure sufficient subjects are enrolled in the 12-16 year old stratum, the 17-19 year old stratum will be capped at a maximum of 90 subjects, leaving at least 210 subjects (approximately 70 subjects per treatment group) in the 12-16 year old stratum.

Efficacy Analysis

The primary efficacy inference for the study is a comparison of varenicline to placebo for the CQR for Weeks 9 through 12. This measure will be obtained through reports of cigarette or other nicotine use since the last study visit confirmed by urine cotinine. An exploratory subgroup analysis for each dosing group by weight stratum for the primary endpoint will be provided.

All efficacy analyses will be performed overall as well as on the subgroup of patients who are 12-16 years of age.

Secondary efficacy endpoints are listed in Section [2.2](#).

These efficacy endpoints will be based on subject self-report, with abstinence confirmed by cotinine.

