6.1.1. Primary Efficacy Endpoint

- *4-week continuous abstinence rate (CA) from Week 9 through Week 12 of treatment for varenicline compared with placebo.*

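### As written, the multiple-imputation rule in SAP 8.2.3 is not limited to missing Week 9-12 outcomes and could replace observed ones for subjects who leave during follow-up

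*SAP*

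**What the plan says.** The primary endpoint is the "4-week continuous abstinence rate (CA) from Week 9 through Week 12 of treatment" (SAP 6.1.1), so no later visit contributes to it. Protocol 5.1 states: "This is a 52 week, double-blind, parallel group study". Protocol 3 and 6.3 describe about nine months of follow-up without treatment after Week 12.

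SAP 8.2.3 introduces multiple imputation as a sensitivity analysis of the effect of missing data on the primary endpoint. It then names two sets of subjects:

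- **Placebo-based:** "Subjects who discontinue the study due to insufficient clinical response, adverse event, or death will be imputed based upon the observed placebo distribution", whatever arm they were randomized to.
- **Own-arm:** "Subjects who discontinue the study for other reasons, or who complete the study but have a missing Week 9-12 CAR, will be imputed" from observed subjects in the same arm.

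Stopping treatment is dealt with in a separate, final sensitivity analysis in the same section. Leaving the study, in the two rules above, therefore does not mean stopping the drug.

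For the primary analysis, SAP 5 and SAP 7 count a subject who leaves as a smoker from the time of leaving onward. The imputation rules contain no such time limit.

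**The concern.** Many trials can use leaving the study as a stand-in for a missing primary outcome, because the two nearly coincide. Here they can be up to 40 weeks apart (52 − 12). A subject may attend every visit in Weeks 9-12, have a known outcome, and withdraw at Week 30. That subject has discontinued the study and so falls into one of the two imputed sets. The authors wrote a missing-outcome condition for completers and none for discontinuers.

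Two things are at stake. First, a check on missing data could discard data that are not missing, and its result would then depend partly on who leaves in Weeks 13-52. Second, even if only missing values are filled, the choice between placebo-based and own-arm imputation depends on a reason for leaving that may arise long after the endpoint window has closed.

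**Working it through.** **1. The plan's own figure.** Inputs are from Protocol 9.1: "the sample size calculation is based on a two-sided Chi-Square test with a 0.05 significance level"; "The sample size is based on CQR of 9% and 24% for placebo and varenicline respectively, or an odds ratio of 3.2"; "100 to varenicline 1 mg BID, 100 to varenicline 0.5 mg BID, 100 to placebo".

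- Mean rate (0.09 + 0.24)/2 = 0.165. Null SE = √(2 × 0.165 × 0.835/100) = 0.0525. Alternative SE = √((0.09 × 0.91 + 0.24 × 0.76)/100) = 0.0514.
- Power = Φ[(0.15 − 1.96 × 0.0525)/0.0514] = Φ(0.916) = 82.0%.
- Odds ratio = (0.24/0.76)/(0.09/0.91) = 3.19.

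This agrees with "The study is powered at 80% or greater". The point does not depend on it; only the two rates are carried forward.

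**2. What the text does with individual subjects.**

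| Week 9-12 outcome | Later course | Literal rule |
|---|---|---|
| Observed | Completes Week 52 | Kept |
| Observed | Leaves at Week 30, adverse event | Imputed from placebo |
| Observed | Leaves at Week 30, other reason | Imputed from own arm |
| Missing | Completes Week 52 | Imputed from own arm |
| Missing | Leaves at Week 40, other reason | Imputed from own arm |
| Missing | Leaves at Week 40, adverse event | Imputed from placebo |

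Rows 2 and 3 are the possible replacement of known outcomes. Row 6 against rows 4 and 5 shows a later event choosing the imputation source.

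**3. Size under the literal rule.** The documents give no follow-up dropout rate. Assume that a fraction f of each arm leaves after Week 12 with the outcome observed, and that no other Week 9-12 outcome is missing. Replaced outcomes = 300 × f.

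- **(a)** All leave for insufficient response, adverse event or death, and abstained as often as stayers. The varenicline rate becomes 0.24(1 − f) + 0.09f; placebo stays at 9%.
- **(b)** All leave for other reasons and abstained as often as stayers. The difference stays at 15 points, but only 100(1 − f) observed outcomes per arm remain.
- **(c)** All leave for other reasons and abstained half as often as stayers. Each arm moves to its stayers' rate, p/[(1 − f) + 0.5f].

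| f | Replaced of 300 | (a) varenicline rate; difference; OR | (b) observed left per arm | (c) placebo, varenicline; difference; OR |
|---|---|---|---|---|
| 10% | 30 | 22.5%; 13.5; 2.94 | 90 | 9.5%, 25.3%; 15.8; 3.23 |
| 20% | 60 | 21.0%; 12.0; 2.69 | 80 | 10.0%, 26.7%; 16.7; 3.27 |
| 30% | 90 | 19.5%; 10.5; 2.45 | 70 | 10.6%, 28.2%; 17.6; 3.32 |
| 40% | 120 | 18.0%; 9.0; 2.22 | 60 | 11.3%, 30.0%; 18.8; 3.38 |

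These are scenarios, not bounds. If 40% leave for other reasons and none of them had been abstinent, the rates become 0.09/0.6 = 15% and 0.24/0.6 = 40%, a difference of 25 points.

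**4. Under the narrower reading.** If only undetermined outcomes are imputed, no observed outcome is replaced and the expected difference stays at 15 points.

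**The case against.** The strongest reply is that the paragraph can be read harmlessly. Its stated purpose is missing data. Its donors are observed subjects, and a subject who leaves at Week 30 with a full Week 9-12 record is an observed subject for this endpoint. Multiple imputation ordinarily fills gaps, and no sentence sets observed outcomes to missing. SAP 5 and SAP 7 treat leaving as acting forward in time. Protocol 9 also refers to a Statistical Rulebook, not available here, that may settle the matter.

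Much of this stands. A reader might infer that the plan orders known outcomes to be overwritten, or that the program will do so. The documents do not support that: keeping observed outcomes is a workable reading. The harmless reading still does not repair the text. Under SAP 5 and 7 an early leaver is coded as a smoker, not as missing. Someone must therefore undo that coding for a defined set before anything can be imputed. For discontinuers, the only set the paragraph defines is by study status and reason, and nothing says observed outcomes are kept. The harmless reading also leaves the dependence on late reasons for leaving untouched.

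It is also fair that the inputs are assumed and that scenario (a) is extreme. Dosing ends at Week 12, and Protocol 6.4 does not make relapse a ground for withdrawal, so exits in the placebo-based class during follow-up may be few. Against sampling error the shifts can look modest: the SE of the log odds ratio at the design rates is √(1/24 + 1/76 + 1/9 + 1/91) = 0.42, and moving from 3.19 to 2.94 is 0.08 on that scale. At 40% in scenario (a) the shift is ln(3.19/2.22) = 0.36. Sampling error is not the right yardstick in any case. The sensitivity and primary analyses use the same subjects, and a gap between them would be read as an effect of missing data.

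**Conclusion.** The point holds as a defect in the stated rule. The imputed sets are defined by leaving a 52-week study, with no Week 12 limit and no missing-outcome condition for discontinuers. The rule could therefore replace observed Week 9-12 outcomes, and it lets a reason for leaving after Week 12 choose the imputation source. Two competent programmers could follow it and report different odds ratios.

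If 10% to 40% leave after Week 12, the literal rule replaces 30 to 120 of 300 known outcomes. The expected difference runs from about 9 points (scenario (a), 40% leaving) to about 19 (scenario (c), 40% leaving), so the distortion can go either way. The dropout range, the reasons for leaving and the leavers' abstinence are all assumptions.

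The scope is one sensitivity analysis. A reader might also infer that the primary analysis counts a Week 30 leaver as a smoker at Week 12, because the responder-rate sentence in SAP 5 has no time limit of its own. The sentence before it, and SAP 7, apply the smoker rule only from the time of leaving, so that inference is not supported. The primary analysis, the order of testing and the sample size are unaffected. The change should be made, but the trial's main conclusion does not turn on it.

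**What to change.** Reword the two imputation sentences in SAP 8.2.3, before unblinding, to say that:

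- only subjects whose Week 9-12 outcome cannot be determined from observed data are imputed;
- every observed Week 9-12 outcome is kept, whatever the date of or reason for later study discontinuation. This includes a subject already known to have smoked within the window before leaving;
- placebo-based or own-arm imputation is assigned by the reason for leaving before the Week 12 assessment;
- subjects with an undetermined outcome who leave after that assessment, or who complete the study, use the own-arm model.

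A short clause in SAP 5 tying the responder-rate sentence to the endpoint's own time window would remove the parallel doubt there.

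The cost is two reworded sentences, one optional clause and a simpler imputation flag. No new data are needed, and the analysis would then match its stated purpose.

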7. ASSESSMENTS

7.1. Efficacy

7.1.1. Smoking Status

Smoking status will be assessed using a standard series of questions referred to as the Nicotine Use Inventory (NUI) ([Appendix 1](#)). The subject responds Yes or No to questions about cigarette or other nicotine/tobacco use since the last visit or during the past 7 days. The NUI is completed at each clinic visit and/or phone contact during the treatment period and the follow-up period by research staff based on subjects' responses.

All subjects will be provided with Smoking Diary Worksheets to use as a tool to record how many cigarettes they have smoked each day. The Smoking Diary itself will not be data-based.

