Appendix 1. Nicotine Use Inventory

Asked at the Week 1 visit through the Week 12 visit

- Has the subject smoked any cigarettes (even a puff) since the last study visit?
- Has the subject used any other nicotine-containing products (eg, nicotine patch, nicotine gum, nicotine nasal spray, nicotine inhaler, nicotine lozenge, pipe, cigars, chew, snuff) since the last study visit?
- Has the subject smoked any cigarettes (even a puff) in the last 7 days?
- If the subject smoked in the last 7 days, has the subject had any days on which no cigarettes were smoked, and if so, how many days?
- If the subject smoked in the last 7 days, how many cigarettes did the subject smoke per day, on average for the days on which smoking occurred?
- Has the subject used any other nicotine-containing products (eg, nicotine patch, nicotine gum, nicotine nasal spray, nicotine inhaler, nicotine lozenge, pipe, cigars, chew, snuff) in the last 7 days?

Asked at the Week 13 visit through the Week 52 visit

- Has the subject smoked any cigarettes (even a puff) since the last contact?
- Has the subject used any other tobacco products (eg, pipe, cigars, chew, snuff) since the last contact?
- Has the subject smoked any cigarettes (even a puff) in the last 7 days?
- If the subject smoked in the last 7 days, has the subject had any days on which no cigarettes were smoked, and if so, how many days?
- If the subject smoked in the last 7 days, how many cigarettes did the subject smoke per day, on average for the days on which smoking occurred?
- Has the subject used any other tobacco products (eg, pipe, cigars, chew, snuff) in the last 7 days?

Additionally Asked on the Week 52 visit

- Has the subject smoked any cigarettes (even a puff) in the last 4 weeks?
- Has the subject used any other tobacco products (eg, pipe, cigars, chew, snuff) in the last 4 weeks?
- Nicotine replacement therapy and/or other smoking cessation medications should be recorded in the concomitant medicine pages in the case report form.

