8.2.4. Secondary Efficacy Analyses

8.2.4.1. The 7-day Point-prevalence of Smoking Abstinence at Weeks 12, 24, and 52

The 7-day point prevalence of abstinence will be summarized by treatment group and visit from Week 3 through Week 52 using descriptive statistics and bar charts.

These will be summarized for the following groups:

- Overall study.
- 12-16 year old age stratum.
- 12-16 year old age stratum, ≤ 55 kg weight stratum.
- 12-16 year old age stratum, > 55 kg weight stratum.
- 17-19 year old age stratum.

The 7-day point prevalence of abstinence at Weeks 12, 24, and 52 will be analyzed using separate logistic regression models as described in [Section 8.1.1.2](#). Odds ratios and 95% confidence intervals will be shown in plots.

These will be analysed for the following groups:

- Overall study.
- 12-16 year old age stratum (without age strata covariate).
- 12-16 year old age stratum, ≤ 55 kg weight stratum (without age strata or body weight strata covariates).
- 12-16 year old age stratum, > 55 kg weight stratum (without age strata or body weight strata covariates).

8.2.4.2. The Reduction in Number of Cigarettes Smoked at Weeks 12, 24, and 52

The reduction in the number of the cigarettes smoked will be calculated at each visit by subtracting the reported average number of cigarettes smoked per day in the past 7 days at each visit from the average number of cigarettes smoked per day in the past 7 days reported at the baseline visit.

The reduction in the mean number of cigarettes smoked per day over the past 7 days will be summarized by treatment group and visit using descriptive statistics.

These will be summarized for the following groups:

- Overall study.
- 12-16 year old age stratum.
- 12-16 year old age stratum, ≤ 55 kg weight stratum.
- 12-16 year old age stratum, > 55 kg weight stratum.
- 17-19 year old age stratum.

The reduction in the mean number of cigarettes smoked per day will be analyzed using longitudinal repeated measures models as described in [Section 8.1.2.2](#). In addition to treatment and visit, baseline number of cigarettes smoked, pooled study center, age strata, and body weight strata will be included as covariates. A treatment by visit interaction will be included for estimation purposes. Least square means and 95% confidence intervals will be shown in plots.

These will be analysed for the following groups:

- Overall study.
- 12-16 year old age stratum (without age strata covariate).

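### The Week 9-12 multiple imputation ignores weekly smoking status, so unequal dropout of smokers between arms can bias its odds ratio in either direction

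*SAP*

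**What the plan says.** The primary analysis counts anyone who leaves the study as a smoker from that point (SAP 5 and 7). As a check on this, SAP 8.2.3 says "multiple imputation methods will be used to evaluate the impact of missing data". It describes two models.

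- **Placebo-draw model**, for those who leave because of insufficient response, an adverse event or death. They "will be imputed based upon the observed placebo distribution, regardless of randomized treatment assignment", and "Imputation will be based on age stratum, body weight stratum, pooled study center, and baseline number of cigarettes smoked".
- **Own-group model**, for the rest: "Subjects who discontinue the study for other reasons, or who complete the study but have a missing Week 9-12 CAR, will be imputed" from observed subjects in their own treatment group, and "Imputation will be based on treatment, age stratum, body weight stratum, pooled study center, and baseline number of cigarettes smoked".

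The only post-baseline information in either model is the reason for leaving, which decides the draw.

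Smoking status is nevertheless collected throughout treatment. Protocol 7.1.1: "The NUI is completed at each clinic visit and/or phone contact during the treatment period". The form asks at Weeks 1 to 12: "Has the subject smoked any cigarettes (even a puff) since the last study visit" (Protocol Appendix 1). The SAP already tabulates a version of it: "The 7-day point prevalence of abstinence will be summarized by treatment group and visit from Week 3 through Week 52" (SAP 8.2.4.1).

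**The concern.** The endpoint is abstinence, so smoking status shortly before dropout is the obvious predictor of the missing value. Without it, the own-group model is justified only if dropout is unrelated to smoking among subjects with the same baseline data in the same arm. Smokers who have failed to quit may well leave more often. The imputed abstinence rate is then too high in an arm that loses many smokers, and the odds ratio is distorted if the arms lose them at different rates. A check meant to show how far the missing-equals-smoker rule can be trusted could then raise a false alarm or give false comfort.

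There is also a gap in wording. SAP 8.2.3 mentions a missing Week 9-12 result only for completers. For discontinuers it does not say that a result already determined by the data is kept.

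**Working it through.** **The plan's own figures.** Protocol 9.1 assumes 9% on placebo and 24% on varenicline: (0.24/0.76)/(0.09/0.91) = 3.19, matching the stated 3.2. The documents give no dropout rates, so every dropout figure below is an assumption.

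**Check 1: status known, dropout depends on status.** Assumed for one varenicline arm against placebo: 40% and 15% abstinent before Week 9; Week 9-12 abstinence 62% if abstinent then, 2% if smoking.

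For each arm, let p be the share abstinent, a abstainer dropout and s smoker dropout:

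- Truth = 0.62p + 0.02(1 − p): 26.0% and 11.0%, odds ratio 2.84.
- Observed successes S = 0.62p(1 − a) + 0.02(1 − p)(1 − s).
- Observed share n = p(1 − a) + (1 − p)(1 − s).
- Primary rule = S. Own-group imputation = S + (1 − n)(S/n) = S/n.

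Example with s = 40% on varenicline and 20% on placebo, a = 8% in both:

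- Varenicline: S = 0.2282 + 0.0072 = 0.2354; n = 0.368 + 0.360 = 0.728; S/n = 32.3%.
- Placebo: S = 0.0856 + 0.0136 = 0.0992; n = 0.138 + 0.680 = 0.818; S/n = 12.1%.
- Odds ratio: imputation 3.46, primary rule 2.80.

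| Smoker dropout, varenicline/placebo | Primary rule (a = 8%/8%) | Own-group imputation (a = 8%/8%) | Primary rule (a = 20%/8%) | Own-group imputation (a = 20%/8%) |
|---|---|---|---|---|
| 30/30% | 2.87 | 2.80 | 2.41 | 2.53 |
| 35/25% | 2.83 | 3.11 | 2.38 | 2.82 |
| 25/35% | 2.91 | 2.51 | 2.45 | 2.27 |
| 40/20% | 2.80 | 3.46 | 2.35 | 3.14 |
| 20/40% | 2.95 | 2.25 | 2.48 | 2.03 |

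Against the true 2.84, with equal abstainer dropout the imputation is further off in every row (at 30/30% by a trivial margin). With 20% abstainer dropout on varenicline it is closer at 30/30, 35/25 and 40/20%, and further off at 25/35 and 20/40%.

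**Check 2: the plan's 9% and 24%.** Suppose every dropout is a smoker. The primary rule is then exact (3.19), and own-group imputation gives true rate/(1 − dropout):

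- Dropout 30% placebo, 10% varenicline: 12.9% and 26.7%, odds ratio 2.46.
- Dropout 10% placebo, 30% varenicline: 10.0% and 34.3%, odds ratio 4.70.
- Dropout 20% in both: 11.3% and 30.0%, odds ratio 3.38.

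Now let dropouts abstain at r times their arm's observed rate. The imputation is further off than the primary rule for r up to about 0.3 to 0.5, depending on the split, and closer above that. With 30% placebo and 10% varenicline dropout, r = 0.4 gives primary 3.58 and imputation 2.78; r = 0.5 gives 3.68 and 2.85.

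**Check 3: last status added to the own-group model** (Check 1 inputs, a = 8% in both). If status is exact, each dropout gets the rate of its own status group and the result is 2.84 by construction. With 10% or 20% of statuses wrong at random:

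- 40/20%: 3.02 or 3.19, instead of 3.46.
- 20/40%: 2.50 or 2.36, instead of 2.25.
- 30/30%: 2.75 for both, against 2.80 without status.

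**Check 4: the placebo-draw model.** At 30/30%, with half of varenicline dropouts drawn from placebo, the planned analysis gives 2.57 against 2.80 for own-group draws. That reduction is intended. With exact status in the model it becomes 2.84 and the penalty is gone; with 10% of statuses wrong it is 2.66 against 2.75, so the penalty is much smaller.

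**The case against.** A reader might infer that the planned imputation is generally worse than the missing-equals-smoker rule. The documents do not support that. Equal 8% abstainer dropout makes the primary rule nearly exact by construction. With more abstainers leaving on varenicline, the planned imputation is closer in three of the five rows. Adverse-event dropout, which the SAP provides for, could produce that pattern. This stands: the direction and the ranking depend on unknown dropout.

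A reader might also want status in both models. Check 4 shows why that is not a plain gain: the placebo draw is meant to be conservative, and status removes or shrinks its penalty.

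Sparse data are a fair objection. With 100 per arm and 30% smoker dropout, the placebo arm has about 9.8 observed successes (8.6 abstainers, 1.2 smokers). A strong predictor beside pooled center may cause separation. The target quit date is Week 1, so the earliest dropouts have little or no useful status.

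The effect is also modest beside sampling error. At the true rates with 100 per arm, the standard error of the log odds ratio is √(1/26 + 1/74 + 1/11 + 1/89) = 0.39; the shifts to 3.46 and 2.25 are 0.20 and 0.23. Both analyses use the same observed subjects, however, so much of that error is shared and does not excuse a bias between them.

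Finally, Protocol 6.4 says that relapse is no ground for withdrawal, and subjects who stop drug are encouraged to stay. This limits smoking-related dropout but cannot exclude it. The further sensitivity analysis by treatment discontinuation does not mention adding smoking status.

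**Conclusion.** The point holds in conditional form. Both imputation models leave out a collected and closely relevant predictor. If smoker dropout differs by arm, the own-group odds ratio is biased upward or downward: under the assumed inputs, 3.46 or 2.25 against a truth of 2.84, where the primary rule gives 2.80 or 2.95. With other equally assumed inputs the imputation is the better of the two (2.82 against 2.38). With equal smoker and abstainer dropout across arms the odds ratio barely moves (2.80), although both rates are overstated (30.0% and 13.3% at 30/30%).

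The figures take abstinence given status to be equal across arms, and compare subjects with the same baseline data. The primary test, the ordered testing and the power calculation are untouched.

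On the wording gap, a reader might infer that the SAP orders determined outcomes to be overwritten. It does not: its stated purpose concerns missing data. It simply leaves the rule for discontinuers unstated.

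**What to change.** 1. Add last observed on-treatment smoking status to the own-group model. Name in advance a penalized or simplified model for use if outcomes are too sparse to fit.
2. Leave the placebo-draw model as the deliberately conservative analysis, or report it with and without status.
3. State that only undetermined Week 9-12 outcomes are imputed. Reported smoking or positive cotinine at a Week 9-12 visit stays non-abstinent (in line with SAP 8.2 on cotinine). A fully observed result is kept for subjects who leave after Week 12 (in line with SAP 5).

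The cost is SAP wording and modest programming, with no new data collection. The limits should be stated. Separation is possible with about 100 per arm. Status before Week 9 is self-report, except where cotinine is taken at an early-termination visit (Protocol 6.2.2). The earliest dropouts contribute little or no status. Imperfect status removes only part of the bias, and with equal smoker dropout the odds ratio may not improve.
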